6.1.5 Storage

Storage will be at 15-25°C at all times. The drug product transit conditions will be 15-25°C using a temperature-monitored and GDP-compliant courier service. See IMP Dossier for stability summary.

6.1.6 Summary of Product Characteristics

Melatonin is an IMP but is not marketed and so there is no SmPC. Please see Appendix 1 and the IMP dossier which provides drug substance and manufacturer information.

6.1.7 Accountability procedures

Drug accountability will be the responsibility of the Clinical Trials Pharmacist.

6.2 PLACEBO

The placebo will be exactly the same in every detail except for the active ingredient (melatonin). For Stage 2, the active drug product will be supplied by APL as for Stage 1 and the placebo will be manufactured by Stockport Pharmaceuticals in the UK and decanted into identical bottles as the active IMP; the bottles will be supplied by APL.

6.3 DOSING REGIME

All patients will receive the trial medication via nasogastric tube or as a drink. In Stage 1 the first cohort of 5 subjects will receive a single dose of 50mg (50ml) and the second cohort of 5 subjects will receive 20mg (20ml) melatonin.

In Stage 2 subjects will be randomised to receive doses of 20mg (20ml) melatonin or placebo at 8 hour intervals. Subjects will receive repeated doses for up to 72h whilst on the ICU or HDU. Patients who are discharged from ICU/HDU before 72h will only receive the trial drug for the duration of the ICU stay. Trial medication of 20mg will be given three times daily for up to 3 days.

6.4 TREATMENT DISCONTINUATION

Treatment will be stopped if a patient develops an unexpected reaction thought to be due to melatonin administration. This might include, but is not limited to, vomiting, diarrhoea or suspected anaphylaxis. There are several expected severe adverse events in this patient population which have been identified in Appendix 3 and it would be any events which are unexpected which we may consider to be criteria for stopping the treatment in an individual patient. If a patient deteriorated due to the underlying disease process it may also be appropriate to discontinue treatment at the discretion of the clinical team. In addition, treatment would be stopped if consent was withdrawn.

6.5 PARTICIPANT COMPLIANCE

Melatonin or placebo will be administered to patients on the ICU/HDU site and will be observed by study personnel. The volume prescribed and the volume given will be recorded in the Case Record File (CRF).

6.6 OVERDOSE

Doses will be prescribed and administered to patients by clinical staff. In Stage 1 subjects will be given only a single dose. If a higher dose than intended is given, or a dose is

given before the intended intervals between doses in Stage 2 then an overdose could perhaps occur. However, there are no previous reports of toxicity from any dose of melatonin and no reports of overdoses. Any patient in whom an overdose occurred would therefore simply be monitored carefully for 24h after overdosing and an adverse event recorded.

6.7 OTHER MEDICATIONS

6.7.1 Permitted Medications

All medication required at the discretion of the clinical team is permitted, except for fluvoxamine or nifedipine. If these drugs were required then no further doses of melatonin or placebo would be given. These drugs interfere with the metabolism of melatonin but are not considered to be harmful to the patient.

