4. STUDY POPULATION

4.1 NUMBER OF PARTICIPANTS

The study will be in two stages:

Stage 1: The first sequential cohort of 5 patients will be assigned to a single oral dose of 50mg melatonin given in a liquid formulation via nasogastric tube or orally as a drink if patients can tolerate this. Usual medical care will be at the discretion of the clinical treating team. Blood samples (10ml) will be obtained prior to melatonin adminstration, after 10 and 30 mins, and 1, 2, 6, 12 and 24h. A second cohort of 5 patients will receive 20mg melatonin and blood will be taken as above.

Once Stage 1 is complete and a dose and dosing interval decision has been made, a substantial amendment will be submitted to update the study protocol accordingly, prior to moving to Stage 2.

Stage 2: In stage 2, 40 patients will be randomised to receive either melatonin or placebo. The dose (20mg) and dosing interval (8 hourly) of melatonin will be based on data from Stage 1. The dose will be based on the maxmimum tolerated dose of melatonin at which first pass metabolism to 6-hydroxmelatonin is complete (20mg). The study will be conducted in a double blind fashion. Melatonin or placebo will be adminstered for 72h or until discharge from ICU or HDU if discharged before 72h. Usual medical care will be at the discretion of the clinical treating team. Subjects will be followed up daily whilst on the ICU/HDU for 5 days then mortality status at 28d will be recorded from medical records.

We propose a 72h dosing period for these reasons: 1. The median length of stay of patients on the ICU in Aberdeen is 4 days. This means that patients will either die or get better in this time frame. 2. Melatonin has been given in other disease conditions for much longer periods even at higher doses with no ill effects. 3. Many previous anti-inflammatory trials in this group of patients have administered trial medication for 72h.

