4.2 INCLUSION CRITERIA (for both Stage 1 and Stage 2)

Adult patients (16 years or over) on the ICU or HDU at Aberdeen Royal Infirmary with sepsis due to community acquired pneumonia who are within 24h of fulfilling the criteria for sepsis with clinical suspicion of pneumonia and the presence of chest X-ray changes consistent with pneumonia will be recruited. The criteria for sepsis are:

- clinical suspicion or evidence of acute infection
- systemic inflammatory response syndrome, defined by two or more of the following:
 - 1. Core temperature <36°C or >38°C;
 - 2. tachycardia: heart rate > 90 beats/min;
 - 3. tachypnoea: respiratory rate > 20 breaths/min or ventilated;
 - 4. leucocyte count >12 x 10^{9} /L or <4 x 10^{9} /L.

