4.3 EXCLUSION CRITERIA (for both Stage 1 and Stage 2)

Subjects will be excluded if they are

- <16 years old,
- have a life expectancy <24h,
- have metastatic cancer or immunosuppression,
- are receiving steroids (>20mg/d prednisolone or equivalent, used regularly for >2 weeks prior to ICU admission)
- women of child bearing potential without a negative pregnancy test or a history of surgical sterilization.
- patients receiving fluvoxamine or nifedipine,
- have overt hepatic failure
- unable to tolerate oral medication
- known to be hypersensitive to trial medication and/or excipients

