6.7.2 Prohibited Medications

Participants will not be recruited if they are taking fluvoxamine or nifedipine.

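### Non-trial melatonin is permitted in both arms: section 6.7.1 excepts only fluvoxamine and nifedipine, and sections 4.3 and 6.7.2 do not bar entry on it

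*Protocol*

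**What the plan says.** Section 6.7.1 gives a general permission with two exceptions: "All medication required at the discretion of the clinical team is permitted, except for fluvoxamine or nifedipine". It adds the consequence, "If these drugs were required then no further doses of melatonin or placebo would be given", and the reason, "These drugs interfere with the metabolism of melatonin but are not considered to be harmful to the patient". Section 6.7.2 applies the same two names at entry: "Participants will not be recruited if they are taking fluvoxamine or nifedipine". Section 4.3 lists "patients receiving fluvoxamine or nifedipine" among its exclusions. It also excludes regular steroids above a threshold and hypersensitivity to trial medication, but not current use of melatonin. Section 4.1 leaves other treatment open: "Usual medical care will be at the discretion of the clinical treating team".

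The sections where a restriction might otherwise sit do not contain one. Section 6.4 (discontinuation) does not mention non-trial melatonin. Section 6.5 (compliance) asks the CRF to record the trial volume prescribed and given. Section 6.6 (overdose) deals with trial doses that are too large or too early.

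**The concern.** Section 6.7.1 is an explicit permission, not silence. Eligibility and permitted medication are fixed in a protocol, so an analysis plan that is not at hand would not normally supply the missing rule. As written, a placebo patient can take the study drug and still be fully compliant.

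This sits badly with the protocol's own reasoning. The two excepted drugs are not thought harmful. They are restricted because they alter how melatonin is handled, and melatonin from another source also alters melatonin exposure.

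Three things are at stake. The summary plans melatonin and metabolite measurements in Stage 2, and section 1.1 wants those levels related to biomarkers. Section 1.1 also wants the degree of biomarker change compared with placebo. Section 9.1 wants the pilot to support the sample size of a later trial. Each is easier to interpret if placebo patients receive no melatonin.

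**Working it through.** The protocol states no power, alpha, effect size or rate of melatonin use, so there is no figure to reproduce. The check is textual, with some counting.

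**1. Is the gap real?** Sections 4.1, 4.3, 6.3 to 6.6, 6.7.1 and 6.7.2 were read together. Among drugs that affect melatonin exposure, only fluvoxamine and nifedipine are named. No section bars melatonin from outside the trial, requires a washout, or asks for its use to be recorded.

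**2. Could it happen?** Section 1.2 says melatonin is used for sleep patterns in blind people and for jet lag, so entry on it is possible. The same section mentions use in ICU patients, but the two references cited are a pharmacokinetic study and a small randomised trial, not routine care. Section 6.1.6 says melatonin is not marketed. That explains the absence of a product summary and does not prohibit use. The frequency is unknown and may be zero.

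**3. How large is one patient?** With 20 per group (section 9.1), 1/20 = 5% of an arm.

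**4. Which samples are open to distortion?** Inputs are sections 6.3 and 7.2.
- Doses: 3 per day × 3 days = 9, at 0, 8, …, 64h if the first is at 0h.
- Samples: pre-dose, 1, 24, 48, 72 and 96h = 6 if day 5 is read as 96h; adding 120h makes 7.
- Time since the last trial dose (64h): 72 − 64 = 8h, 96 − 64 = 32h, 120 − 64 = 56h. If a tenth dose is given at 72h, the last two become 24h and 48h.
- In healthy subjects the metabolite was still raised at 6h and back to baseline at 24h (section 1.1). On that basis the 96h and 120h samples lie outside trial exposure. Clearance in sepsis may be slower.

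| Arm | Samples without trial melatonin |
|---|---|
| Placebo | 6 of 6, or 7 of 7 |
| Melatonin | pre-dose and 96h: 2 of 6; with 120h: 3 of 7 |

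These counts show where distortion could occur, not how much. All placebo samples would be affected only if use continued throughout. A patient who stopped at admission would mainly affect the baseline. Section 4.1 adds: "The median length of stay of patients on the ICU in Aberdeen is 4 days". That figure is not specific to sepsis and does not cover HDU stay, but it suggests that roughly half of patients may leave before a 120h sample.

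**5. What happens to the biomarker contrast?** Trial exposure is 3 × 20 = 60mg/day. Assume equal non-trial use of x mg/day in both arms and an effect proportional to dose. The contrast is then (60 + x) − x = 60mg/day, so there is no dilution and the sample size inflation is 1.00. Unequal use or a non-proportional effect would change this, but the document gives no basis for either.

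**6. How large is a sleep dose?** Section 1.1 puts sleep-wake doses at 1–5mg. Taken once daily, that is 1/60 = 1.7% to 5/60 = 8.3% of the trial dose. The DMC charter's ceiling for low doses, under 10mg, would be under 10/60 = 16.7% if taken once daily.

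**The case against.** The strongest reply is that the problem may never arise and would be small if it did. No use at the site is shown. Section 1.1 says antioxidant and anti-inflammatory actions need doses considerably above those used for sleep. Both points stand, and they limit the size of the concern.

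A second reply is that section 2.2 lists no melatonin level among the Stage 2 endpoints, section 7.2 takes Stage 2 blood for the measures in 2.2, and section 9.2 describes concentration-time analysis only for Stage 1. This is fair. Even so, the summary and the objectives in the DMC charter both plan melatonin and metabolite measurements, and a small dose can still move a placebo or baseline level.

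A third is that the two named drugs change the handling of every trial dose, whereas extra melatonin adds to it. The mechanism does differ, so carrying the protocol's reason over to melatonin is an inference. What they share is a change in melatonin exposure that randomisation did not assign.

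Fourth, in-unit prescriptions would normally appear on the ICU/HDU charts from which section 8 draws clinical data. That might reveal use afterwards, but no CRF field for it is specified and nothing would prevent it.

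A reader might go further and infer that the treatment contrast is diluted and power lost. With an assumed 80% power at two-sided 0.05 and 20 per arm, and with 5% to 20% of placebo patients getting the full trial effect, power would fall to 76% to 61%. The document does not support this. It states no power, the rates are invented, and a full effect from a sleep dose conflicts with section 1.1.

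**Conclusion.** The point holds as an advisory one. The protocol lets patients in either arm enter on, or be prescribed, non-trial melatonin without a deviation. That much is certain from the text; its practical importance is not. Frequency is unknown and possibly zero, and the Stage 2 endpoint of recruiting 40 patients and completing evaluation is untouched. No biomarker dilution or loss of power can be derived. What remains is possible distortion of melatonin and metabolite levels, mainly in placebo patients and at baseline, and a placebo condition less clean than it need be. The sample counts assume the healthy-subject return to baseline by 24h. For Stage 1 the point has little force, because this version already fixes 20mg every 8 hours from Stage 1 data.

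**What to change.** - In 4.3 and 6.7.2, add current use of non-trial melatonin to the exclusions. No washout is needed, so the entry window in 4.2, "within 24h of fulfilling the criteria for sepsis", is not affected.
- In 6.7.1, prohibit non-trial melatonin until the last blood sample (up to day 5).
- In the same section, state that if it is given anyway, trial dosing continues, the use is recorded in the CRF with dose and time as a deviation, and the patient stays in the intention-to-treat analysis.

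The last item matters because the existing sentence, "If these drugs were required then no further doses of melatonin or placebo would be given", would otherwise appear to apply. Ending a 60mg/day regimen because of one low sleep dose would lose more contrast than the rule protects.

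The drafting cost is a line in each of 4.3 and 6.7.2, a short addition to 6.7.1 and one CRF field. The downside is that a few current users become ineligible at a single site that must recruit 40, and the clinical team must use another sleep aid up to day 5.

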6.7.2 Prohibited Medications

Participants will not be recruited if they are taking fluvoxamine or nifedipine.

7. STUDY ASSESSMENTS

7.1 SAFETY ASSESSMENTS

Patients will be monitored continuously with usual nursing care.

7.2 STUDY ASSESSMENTS

Recruited subjects will be Intensive Care Unit or High Dependency Unit patients.

Stage 1: The first sequential cohort of 5 patients will be assigned to a single oral dose of 50mg melatonin given in a liquid formulation via nasogastric tube or as a drink. All other clinical treatment will be at the discretion of the clinical team. Blood samples (10ml) will be obtained prior to melatonin adminstration, after 10 and 30 mins, and 1, 2, 6, 12 and 24h. A second cohort of 5 patients will receive 20mg melatonin and blood will be taken as above. Concentrations of melatonin and 6-hydroxymelatonin will be analysed as detailed in section 2.3 above.

Stage 2: In stage 2, 40 patients will be randomised to receive either 20mg (20ml) melatonin or placebo. The study will be conducted in a double blind fashion. Melatonin or placebo will be adminstered for a maximum of 72h or until discharge from ICU/HDU if <72h, and subjects' 28d mortality status will be recorded. Blood samples (10ml) will be taken prior to study drug adminstration, and after 1, and 24h, then daily during the ICU stay up to a maximum of 5 days for the measures as detailed in Section 2.2. Blood samples taken solely for research purposes will be taken from existing cannulae into appropriate blood sampling tubes and processed on the ICU by a trained research nurse and placed into a dedicated -20°C freezer on the the ICU. They will then be transported to the research laboratory in the Institute of Medical Sciences for storage at -80°C according to Standard Operating Procedures in a dedicated freezer in the laboratory. Routine blood tests taken as part of usual medical care will be handled and processed as usual and results of these will be recorded. Processes for sending samples off site for analysis will comply with a pre-defined Material Transfer/Technical Agreement and the agreed Analytical Protocol according to UoA-NHSG-SOP-022. These samples will be stored in Aberdeen until all samples are collected then sent by courier on dry ice for analysis. Remaining samples (if any) will be returned to the Chief Investigator after analysis is complete for sample reconciliation and disposal or storage records to be maintained.

Heart rate, mean arterial pressure, temperature, acute physiologial and chronic health evaluation (APACHE) II score, will be recorded at least daily during the ICU/HDU stay

for up to 5 days. Length of ICU/HDU stay, ICU/HDU- and 28 day- all cause mortality will be recorded.

8. DATA COLLECTION

Clinical data will be collected from ICU/HDU charts and entered into a CRF. Biochemical and pharmacokinetic data will be reported to the Chief Investigator and the research team at the end of Stage 1. For Stage 2 biochemical data will be reported to the Chief Investigator and the research team at the end of Stage 2. stage and will be recorded on a dedicated trial database.

9. STATISTICS AND DATA ANALYSIS

9.1 SAMPLE SIZE CALCULATION

For Stage 1 data analysis will be simple descriptive statistics for pharmacokinetic data in each dose cohort, to include Cmax, Tmax, AUC and time to return to baseline for both melatonin and 6-hydroxymelatonin. For Stage 2, as a pilot, this study does not require a formal sample size calculation. Although melatonin levels after a single oral dose can be variable, as explained the levels of 6-hydroxymelatonin are less variable and are also bioactive. We therefore anticipate that 20 patients per group will allow an initial exploration of potential effects to enable a formal sample size to be calculated for a definitive subsequent trial.

9.2 PROPOSED ANALYSES

Melatonin and 6-hydroxymelatonin will be measured in house using liquid chromatography-tandem mass spectrometry (LC-MS/MS) and enzyme immunoassay respectively. These methods have been established and validated in-house. For stage 1, concentration-time data will be used to determine peak concentrations in serum, time to peak concentration in blood, minimum concentration in serum, area under the serum concentration-time curve from immediately prior to dosing to the last sample and extrapolated to infinity, the apparent terminal elimination half-life. Summary statistics will be reported for all pharmacokinetic parameters, weight, age and clinical data. Intention to treat analysis will be undertaken.

Arterial blood lactate will be analysed on the ICU using blood gas analysers in routine use. CRP will be measured by the Pathology Department as is routine. Other biomarkers will be measured in house using luminex multiplex technology, to include tissue specific injury markers, cytokines, adhesion molecules and chemokines: MCP-1, Endocan, IL-1 beta, IL-2, IL-4, IL-6, IL-8, IL-18, Pentraxin 3, E-Selectin, SP-D, uPAR, VCAM-1, IL-10. As part of the multiplex biomarker analysis, linear discriminant analysis, hierarchical regression and hierarchical cluster analysis will be used to explore relationships between biomarkers and other indices and will provide useful information regarding proxies of patient outcome for both this and future studies.

Blood will be treated to stabilize gene transcription and then stored at -70°C. Total RNA will be extracted at a later date and purified for analysis of mRNA by the University of Aberdeen Genome Centre. Bioinformatic analysis will include quality control, normalisation, fitting of statistical models to identify differentially expressed features and downstream analysis such as gene set enrichment.

Any data analyses will be pre-specified and governed by a comprehensive analysis plan finalised before analysis begins, which will be authored by [name]. The primary analyses will be on an intention to treat basis. Broadly the plan will investigate initial exploratory data and descriptive analyses followed by appropriate univariate analyses to examine the two groups (melatonin and placebo) for the various measurements and patient characteristics. These will be put together along with baseline co-variates, confounders and effect modifiers, defined *a priori*, into appropriate multiple regression models. Multilevel Linear Modelling will be conducted including variables with measurements taken over time thus allowing for related measures at potentially irregular time intervals.

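### Section 9.2 applies intention to treat to the Stage 1 pharmacokinetic summaries, so an incompletely dosed patient would be summarised under the assigned dose

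*Protocol*

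**What the plan says.** Section 4.1 describes Stage 1: "The first sequential cohort of 5 patients will be assigned to a single oral dose of 50mg melatonin", followed by "A second cohort of 5 patients will receive 20mg melatonin and blood will be taken as above". Section 3 calls it an open-label cohort study; randomisation (section 5.5.1) belongs to Stage 2. Sampling runs from before the dose to 24h after it.

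Section 9.2 introduces the analysis with "For stage 1, concentration-time data will be used to determine peak concentrations in serum, time to peak concentration in blood, minimum concentration in serum", adds AUC and half-life, and closes the paragraph with "Summary statistics will be reported for all pharmacokinetic parameters, weight, age and clinical data. Intention to treat analysis will be undertaken". Later in section 9.2, where the melatonin and placebo groups are compared, intention to treat is stated again: "The primary analyses will be on an intention to treat basis".

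Three other sections bear on whether an assigned dose was really received:
- Section 6.4 gives examples of reactions that would stop treatment: "This might include, but is not limited to, vomiting, diarrhoea or suspected anaphylaxis".
- Section 6.5 has both the prescribed and the administered volume entered in the CRF.
- Section 6.7.1 says of fluvoxamine and nifedipine: "These drugs interfere with the metabolism of melatonin". If either is needed, the rule is to give no more trial medication.

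Replacement of patients appears only under withdrawal (section 5.5.4).

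**The concern.** Intention to treat protects a randomised comparison. Stage 1 has none. Its research questions (section 1.2) ask what concentrations each dose produces and for how long, which presupposes that the labelled dose was given and kept down. Under intention to treat, a patient assigned 50mg who receives or retains only part of it still counts as a 50mg profile.

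The protocol anticipates the relevant events but does not connect them to the pharmacokinetic analysis. Vomiting is only a reason to stop treatment. The volume given is recorded, but the stated principle makes no use of it. The rule for interacting drugs has no effect once the single Stage 1 dose has been given. The replacement provision does not reach a patient who was under-dosed but stays in the study.

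At stake is the accuracy of Cmax, AUC and related values reported from cohorts in which each patient is one fifth of the data. These values underlie the Stage 2 regimen and may be carried into the larger trial that this study is meant to inform.

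**Working it through.** **No figure to reproduce.** The protocol gives no calculation for 5 per cohort and no numerical target for Stage 1.

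**Inputs from the protocol.** n = 5 per cohort and doses of 50mg and 20mg (section 4.1); summary type unspecified (sections 9.1 and 9.2).

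**Assumed inputs.** The documents give no rate of vomiting, partial dosing or new interacting medication, and neither the size nor the direction of the interaction. So f (an affected patient's exposure relative to an otherwise similar patient) and p (the chance that a patient is affected) are shown as ranges.

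**Shift in the cohort summary.** With k of 5 patients affected and the others equal:
- arithmetic mean: k(f-1)/5
- geometric mean: f^(k/5) - 1

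| k | f | Arithmetic mean | Geometric mean |
|---|---|---|---|
| 1 | 0 | -20% | not computable |
| 1 | 0.25 | -15% | -24.2% |
| 1 | 0.5 | -10% | -12.9% |
| 1 | 0.75 | -5% | -5.6% |
| 1 | 2 | +20% | +14.9% |
| 2 | 0 | -40% | not computable |
| 2 | 0.5 | -20% | -24.2% |

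For example, with k = 1 and f = 0.5: (0.5-1)/5 = -0.10, and 0.5^0.2 - 1 = -0.129. In this simple case the median of 5 does not move with one or two patients affected.

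**Comparison of the two cohorts.** If exposure is proportional to dose (an assumption), the ratio of means should be 50/20 = 2.5. One 50mg patient with f = 0 gives 2.5 × 4/5 = 2.0. One 20mg patient with f = 0 gives 2.5 ÷ (4/5) = 3.1. With f = 0.5 the ratios are 2.25 and 2.8.

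**Chance that it arises.** P(at least one affected) = 1 - (1-p)^n. For p = 5%, 10% and 20% this is 23%, 41% and 67% in one cohort of 5, and 40%, 65% and 89% across both cohorts.

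**Against sampling error.** The standard error of a mean of 5 is CV/√5: 13.4%, 26.8% and 44.7% for assumed CVs of 30%, 60% and 100%. A shift of 10% to 20% is therefore similar to or smaller than the noise. Unlike the noise, it can be avoided.

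**The case against.** The sentence names no stage. Its paragraph opens with assay methods that are not limited to Stage 1, and the preceding sentence also covers weight, age and clinical data. It could be a loosely placed general remark. That is possible, but the paragraph's analysis content is introduced as Stage 1, and intention to treat is stated separately for the primary analyses. The plain reading therefore remains that it covers the Stage 1 summaries.

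An evaluable set and rules for vomiting are often left to an analysis plan, and section 9.2 promises one. Silence on those details would be no fault. The point here is different: the protocol states a principle that does not fit, and an analysis plan that followed it would inherit the problem.

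The triggers are narrow. Patients on fluvoxamine or nifedipine, or unable to tolerate oral medication, are excluded at entry, and dosing is observed. This stands, and only events after enrolment in 10 patients matter.

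Two stronger readings are tempting. A reader might infer that the plan commits to averaging under-dosed patients as if fully dosed, so that means of 5 will be biased. The protocol specifies no mean, and a median would be far more robust. A reader might also infer that the Stage 2 regimen is compromised. The documents do not show that any such event occurred. Section 4.1 bases the dose on tolerability and complete first-pass conversion to the metabolite, not on a contrast of cohort mean AUCs. The DMC's review was a further check, and the regimen is already written into the current text.

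**Conclusion.** The concern holds as a mismatch between a stated analysis principle and the question Stage 1 asks. If an arithmetic mean is reported, one affected patient in 5 moves Cmax or AUC by 20% of the difference between that patient's exposure and the others': -20% with nothing absorbed, -10% with half, +20% if exposure doubled. These sizes rest on assumed values of f, and the probabilities on assumed rates. The interaction limb is illustrative only, since the documents do not say which way or how far exposure would change.

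The practical effect is limited to the reported Stage 1 pharmacokinetics and their later use. It does not reach the randomised comparison, for which intention to treat is appropriate.

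**What to change.** Amend section 9.2 so that intention to treat refers only to the randomised Stage 2 comparison. For Stage 1:
- Base the main pharmacokinetic summary on patients whose full prescribed volume was delivered and retained and who received neither fluvoxamine nor nifedipine during sampling.
- Set the criteria without reference to the measured concentrations. Setting them before any assay result is seen is probably no longer possible, because the current text already reflects the Stage 1 decision.
- Keep patients whose absorption was poor because of sepsis itself; that is part of the pharmacokinetics in the target population.
- List each excluded patient individually with the volume given and the reason.
- Show all dosed patients as a sensitivity summary, and keep all treated patients in the safety summary.

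The cost is a few sentences. The volume given is already in the CRF. The protocol does not say that the time of vomiting is recorded, so it may have to come from the ICU/HDU charts. The downside is that a cohort may fall below 5 evaluable patients, for example to 4, with the fifth profile reported separately.
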